### **3.16 Statistical Analyses**

The primary outcome will be analyzed per intent-to-treat principles as a time to event analysis. For incident dialysis patients, time 0 will begin at day 90 as all patients are provided nutritional supplements during the first 90 days of hemodialysis. Hospitalization and infection will be analyzed as multiple events as well as using a time to first event approach. There are a large number of patients in this study, and it is unlikely that mortality risk factors will be differentially distributed across treatment arms; however, we will evaluate the distribution of key facility and patient factors by allocation group and, if there are differences in these parameters, secondary analyses using multivariable regression will be performed.

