### **3.4 Blinding**

Patients, investigators, and dialysis unit physicians and staff will not be blinded to study arm assignment. The endpoints committee will be blinded to facility (and therefore patient) treatment assignment.

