### **3.6 Recruitment**

The study intervention is considered minimal risk given the nature of the intervention (roughly comparable to the amount of protein consumed with 2 large hard boiled eggs). To achieve

adequate power to evaluate mortality, we will need to recruit more than 5000 HD patients; this will require participation of more than 80 dialysis units throughout DCI, which nationally provides hemodialysis care to approximately 13,000 individuals. Given the pragmatic design of the trial, the high risk of cross-contamination between the usual care and the intensive intervention due to patient-patient interactions, other patient observed patient-dietician and patient-dialysis staff interactions, and our plan to promote the study to the entire facility, it is not practicable to conduct this research without a waiver of informed consent documentation.

Following education of facility staff, patients will receive study information sheets. Patients will have the opportunity to review the study information sheets and ask any questions they may have by contacting the study staff listed in the information sheets. Dialysis staff will note whether the patient agrees to be in the study by documenting it in their medical record. The process for initiating study sites is as follows:

- 1) Send the trial protocol to the governing body for each dialysis facility that is a potential trial participant. The governing body, which typically consists of the facility medical director(s), administrator, nurse manager(s) and chief technician, will review the protocol and have an opportunity to discuss the trial with the PI and central study personnel. Following this, they will need to approve of their facility's participation in the trial before their facility can be considered for inclusion.
- 2) Dialysis staff will participate in one to two pre-study conference calls, receive local facility materials such as posters and patient information sheets, and, at their discretion, have the opportunity to participate in study-wide conference calls that will occur monthly during the first several months of the trial before becoming quarterly thereafter.

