- 3) All patients receiving dialysis in a participating facility prior to the start of the trial (but after the facility has been assigned randomly to a study arm) will receive an information sheet about the trial. These will be made available in multiple languages and will also be available to patient proxies. Information sheets and posters will also be posted in clinical areas of the dialysis facility. As with other information that is communicated to patients as a part of clinical practice, facility personnel will read forms to visually impaired or illiterate patients. All new patients who initiate dialysis at a participating facility will receive the information sheet that applies to their clinic at their initial treatment in the facility and will be asked whether they wish to participate

- 4) Patients can withdraw from the study at any time, regardless of intervention arm, by informing personnel at the dialysis unit that they do not want to take supplements or by simply not taking the supplement.

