### **3.8 Randomization:**

Facilities will be randomized 1:1 to study arms, blocked by region and facility size (small, medium, large). If possible, randomization will occur concurrently for all participating facilities and with protocols available for prescribing immediately by physicians in the facility in the medical information system. Alternatively, depending on the time needed for facilities to approve the trial, we will randomize facilities over several months. Randomization will be performed by DCI's

Information Services (IS) personnel. DCI's IS personnel have experience with randomized clinical trials (RCTs), having designed and overseen an electronic algorithm that randomized patients to treatments arms across 3 strata in a past RCT conducted within DCI. They will create the master file of the treatment assigned to each facility. During the course of the trial, although facilities and patients and providers at those facilities will know their own randomization assignment, this information will not be made widely available to other dialysis units, physicians, patients, or staff, with the exception of the Data Safety Monitoring Board.

Approximately within four weeks following randomization, either treatment to usual care will be continued or treatment to the intensive protocol will begin depending on which protocol the unit has been assigned to as well as whether the patient agreed to be in the study. This gap is to allow sufficient time for patients in facilities to receive and review the information sheets as well as allow for educational materials to be posted in dialysis facilities.

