#### **3.15 Regulatory Issues**

The NIH-sponsored TiME trial sets a useful important precedent for the conduct of large, pragmatic clinical trials in the dialysis setting, an environment that is unique in healthcare due to the frequent contact between patients and the dialysis facility, the continuous interactions among patients, and

the lack of evidence base to guide treatment decisions. The proposed trial comparing two different nutritional supplement strategies follows the spirit of Sugarman and Califf in their recent viewpoint in JAMA describing the role of pragmatic clinical trials in evidence generation to inform care practices. This study will be requesting a waiver of documentation of consent.

1. *The research involves no more than minimal risk to subjects.*

The most common currently utilized oral nutritional supplement within DCI is Prostat. Pro-Stat is a sugar free liquid protein supplements (medical food), with protein derived from hydrolyzed collagen. In our review at DCI of observational data using a natural experiment to inform a pseudo-randomization cohort design, we found impressive benefits and, critically, no sign of harm associated with Prostat use. Similarly, using similar methodology, Lacson and colleagues found impressive benefits and, critically, no signal of harm with four different protein supplements, including Prostat and ZonePerfect Protein bars. Both Pro-Stat and BodyQuest Protein Ice Cream have very low sodium, potassium and phosphorus content, while ZonePerfect bars selected will be their lowest phosphorus and potassium containing options.

For patients in the intensive supplement group, many will receive more doses of the oral nutritional supplement than they otherwise would have received with usual care. There is no known risk associated with the intake of these supplements. Although there are data in pre-dialysis populations suggesting that high protein intake may be associated with more rapid progression of kidney disease and more uremic symptoms, for patients treated with hemodialysis, this concern is no longer present.

For patients in the usual care group, there is no effect of trial participation on medical care and the risk of loss of confidentiality is minimal. These patients will still be allowed to consume other food items during dialysis as they had previously and will still be administered an oral nutritional supplement if their serum albumin is low.

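### Section 3.16 relies on patient numbers for balance, but patients agree after their facility's arm is known, and the intent-to-treat set is not defined

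*Combined protocol and SAP*

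**What the plan says.** Section 3.16 plans an intent-to-treat, time-to-event analysis of all-cause mortality. On baseline balance it says: "There are a large number of patients in this study, and it is unlikely that mortality risk factors will be differentially distributed" across arms. It will compare key facility and patient factors by arm, without naming them, and "if there are differences in these parameters, secondary analyses using multivariable regression will be performed".

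The order of events is set out elsewhere:

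- **Section 3.6 Recruitment, item 3.** Patients already on dialysis are informed before the trial starts, "but after the facility has been assigned randomly to a study arm) will receive an information sheet about the trial". For later arrivals, "All new patients who initiate dialysis at a participating facility will receive the information sheet that applies to their clinic", and they are then asked whether they wish to join.
- **Section 3.6.** "Dialysis staff will note whether the patient agrees to be in the study by documenting it in their medical record".
- **Section 3.4 Blinding.** "Patients, investigators, and dialysis unit physicians and staff will not be blinded to study arm assignment".
- **Section 3.8 Randomization.** Within about four weeks treatment continues or begins, "depending on which protocol the unit has been assigned to as well as whether the patient agreed to be in the study".
- **Section 3.15 Regulatory Issues.** "For patients in the usual care group, there is no effect of trial participation on medical care", whereas many patients in the intensive group will get more supplement than they otherwise would.

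The end of section 2.4 and section 3.15 say that the waiver sought covers documentation of consent, not consent itself.

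**The concern.** Randomizing facilities protects the comparison of all patients at those facilities. It does not automatically protect the comparison of patients who agreed, if they agreed knowing the arm and if agreement had different consequences in the two arms. Should decliners differ in mortality risk and decline more often in one arm, that difference enters the hazard ratio. A larger trial would estimate the distorted value more precisely.

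The planned safeguard is limited. Adjustment is triggered by the data, uses factors not yet named, and cannot correct for unmeasured differences. What is at stake is the interpretation of the mortality result in either direction.

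**Working it through.** **1. The plan's own sample size (section 3.9.1).** Inputs: hazard ratio (HR) 0.85, 80% power, two-sided 0.05, usual-care hazard 0.173, 3 years, dropout 0.05 per arm, intraclass coefficient 0.01, mean facility size 65.

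- Events: 4 × (1.960 + 0.842)² / (ln 0.85)² = 1189.
- Patients, with exponential survival and dropout read as 5% per year: 3348, against 3351 stated.
- Design effect: 1 + 64 × 0.01 = 1.64, and 3351 × 1.64 = 5496, against about 5500.
- Interim inflation: 5500 × 1.017 = 5594, against 5597.

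The arithmetic reproduces, so the sample size is not at fault.

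**2. What drives the bias, if only agreers are analysed.** Let r_I and r_U be the shares declining in the intensive and usual-care arms, and k the mortality of decliners relative to agreers. To first order, with no true effect:

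apparent HR = [(1 − r_U) + r_U·k] / [(1 − r_I) + r_I·k]

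The number of patients does not appear. If r_I = r_U with the same k, the ratio is 1. If all eligible patients are analysed, declining removes nobody and this bias does not arise.

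**3. A benchmark.** Section 3.11 gives a final p-value threshold of 0.0456, so z = 1.999. The drift is (1.960 + 0.842) × √1.017 = 2.825. The largest HR significant at the final analysis is exp(ln 0.85 × 1.999 / 2.825) = 0.891. If the expected estimate is 0.891, power is about 50%.

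**4. Near the worst case: r_U = 0, r_I = d.** The documents give no agreement rates. For d, I borrow the 10–20% supplement refusal in section 3.2, purely as an assumption. First-order solutions are k = (1/0.891 − 1 + d)/d for no true effect and k = (0.85/0.891 − 1 + d)/d for a true HR of 0.85. The Cox limit is solved numerically with exponential hazards and a usual-care mean of 0.173 over 3 years.

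| d | k needed to show 0.891 with no true effect: first-order / Cox limit | k needed to turn a true 0.85 into 0.891: first-order / Cox limit |
|---|---|---|
| 0.10 | 2.22 / 2.63 | 0.54 / 0.58 |
| 0.20 | 1.61 / 1.68 | 0.77 / 0.78 |

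Hiding the designed effect thus needs decliner mortality 42% lower (10-point gap) or 22% lower (20-point gap) than that of agreers.

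**5. Half as much declining in usual care, by the same kind of patients.** Taking 0.173 as the mean hazard of all patients, the Cox limit gives k = 5.3 (10% v 5%) and 2.4 (20% v 10%) to show 0.891 with no true effect. Hiding a true 0.85 needs mortality 73% and 38% lower.

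**6. Sensitivity of the planned balance check.** Section 3.16 does not say how a difference will be judged. Assume a 5% test and an intraclass coefficient of 0.01 for baseline factors. Patients per arm: 5597/2 = 2798.5. Standard error of a standardized difference: √(2 × 1.64 / 2798.5) = 0.034. A difference is flagged from 1.96 × 0.034 = 0.067 SD. In the setting of step 4, decliners must then differ from agreers by 0.67 SD (d = 0.10) or 0.34 SD (d = 0.20). Smaller selection can pass unflagged.

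**The case against.** - **The analysis is intent-to-treat.** If that means every eligible patient at a randomized facility, agreement cannot bias the comparison. This stands as far as it goes, but 3.16 does not say so. Agreement that gates treatment (3.6, 3.8), with only its documentation waived, suggests agreers only. A reader might also take the mention of consented patients in section 3.13 as defining the primary set. It does not: it concerns how much follow-up the last entrants will have.
- **The arms look alike when new patients are asked.** Supplement is given in both arms for the first 90–120 days (3.9.1; 90 days in 3.13 and 3.16). A reader might infer that dislike of the taste is a reason to decline only in the intensive arm; for new patients these sections do not support that. What differs is later care and the arm-specific materials (3.3). Section 3.2 adds that 20–30% of patients receive supplement at any given time under current practice.
- **The 10–20% is refusal of the product, not of the study.** Correct. Someone who dislikes it can join and leave it untaken (3.6 item 4), so a one-sided gap of that size is near the worst case.
- **An unadjusted primary analysis is legitimate.** Agreed. Naming covariates in advance improves the plan; it does not correct an error in the primary analysis.

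**Conclusion.** The point holds in a limited form. The patient-numbers argument does not address selection after allocation, the order of events leaves room for it, and the plan does not say which patients make up the intent-to-treat set. A reader might conclude that the mortality comparison is biased. The documents do not show that: they give neither agreement by arm nor the risk of decliners, and both size and direction are unknown.

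Under the assumptions above, imitating a significant benefit needs strong selection: decliner mortality about 1.7 to 2.6 times that of agreers even with a one-sided gap of 20 or 10 points, and more if usual care also loses such patients. Hiding the designed effect needs a smaller contrast. These figures apply only if agreers alone are analysed.

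**What to change.** Revise section 3.16 as follows.

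1. State whether the intent-to-treat set includes patients who did not agree, and remove the argument from patient numbers.
2. Replace the conditional adjustment with a model that is always fitted, allows for facility clustering and is reported beside the primary result. Name its baseline factors now from routine data: for example the case-mix factors in the Figure 3 legend of section 2.3 (age, sex, race, diabetes, dialysis vintage) plus baseline albumin.
3. If the set is agreers only, and if the IRB allows it, add a sensitivity comparison of mortality among all patients treated at the randomized facilities regardless of agreement. Deaths are already reconciled monthly at each facility (section 3.7).

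The cost is a few sentences, modest analysis work and IRB agreement for item 3. Recruitment is unaffected, so the change can still be made although an interim analysis has taken place. One limit should be stated with item 3: no section says that eligibility is recorded for patients who did not agree, so their eligibility, day-90 time zero and person-time may be only approximate. That makes it a check on the primary result and not a substitute for it.

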##### **2.1 Protein Catabolism during Hemodialysis**

The dialysis procedure itself results in amino acid loss. In several elegant balance studies of hemodialysis patient volunteers, Ikizler and colleagues demonstrated that:

1) Muscle catabolism occurs during dialysis in people not given oral or intravenous protein during dialysis; 2) Plasma amino acid levels drop during hemodialysis in the absence of protein supplementation and do not return to normal immediately post hemodialysis while being maintained near normal in participants being given oral nutritional supplements (Figure 1); and 3) A low dose of amino-acid supplementation can adequately counteract HD-associated catabolism. In

our proposed pragmatic clinical trial, noting these results and the loss of amino acids from the circulation, we will replace estimated losses with 15 g of protein administered during dialysis.

Critically, as shown by Sundell and colleagues, the protein loss and subsequent catabolism induced by hemodialysis is potentially modifiable and represents an attractive target for interventions to improve the overall prognosis and well-being of patients with kidney failure treated with

[figure not shown]

Figure 1. Box-and-whisker plot of changes in total amino acid (TAA) levels ( $\mu\text{mol/L}$ ) during HD vs pre-HD (left plots) and post HD-pre-HD (right plots). Open boxes represent the control group that received no nutritional supplements, light gray boxes represent Pro-Stat lower dose group, and dark gray boxes represent Pro-Stat higher dose group.

maintenance dialysis, with prevalence ranging from 18-75%. Although neither sensitive nor specific, serum albumin, the most prevalent protein circulating in the body, is the most common marker used to estimate nutritional status, and a low serum albumin level, which may indicate both poor nutritional status and heightened systemic inflammation, is a powerful marker of increased mortality risk.

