### **3.2 Intervention**

#### **1. Usual Care versus Intensive Protocols**

Facilities will be cluster randomized into one of two protocols:

- a. Usual care protocol which will continue the current nutritional supplement protocol for all patients at the dialysis facility, whereby those with albumin below 3.5 g/dL receive supplement
- b. Intensive nutritional supplement protocol, which will prescribe nutritional supplements for all patients at the dialysis facility regardless of serum albumin levels

The majority of DCI facilities currently have the majority of their patients prescribed the usual care oral nutritional supplement protocol, with 20-30% of patients at any given time receiving an in-center oral nutritional supplement. Of note, all patients are offered the protocol, but approximately 10-20% refuse the protein supplement, often due to taste and individual preference. Being prescribed the protocol does not affect a patient's ability to consume food or other supplements of their choosing before, during (depending on facility and state regulations) or after dialysis; it simply means that they receive an oral nutritional supplement for consumption during dialysis from the dialysis facility included as a part of their routine dialysis care. The specific nutritional supplement is not specified in the protocol, although many facilities currently use Prostat due to pricing and availability. The protocol prescribes approximately 15 g of oral protein supplement; when Prostat is used, this is accomplished by drinking 30 mL of Prostat. In cases of facility or patient preference, including taste fatigue, other supplements can be used in the current usual care protocol in lieu of Prostat (as was the case in the quality improvement report published by Lacson and colleagues). For example, the PI's facility currently has some patients receiving Prostat while others receive BodyQuest Protein Ice Cream, reflecting patient preference. Nutritional supplements utilized during the trial will vary, but should contain approximately 15 g (range 12 to 20 g) of protein with low sodium, potassium and phosphorus content. Based on current use within DCI and availability as well as prior experiences and cost, we anticipate the following protein supplements will be utilized:

- a) BodyQuest Protein Ice Cream, which contains 16 g of protein and 120 kcal per serving
- b) Prostat, Sugar Free, which contains 15 g of protein and 100 kcal per serving

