## 2. Implementing the Intervention

As occurs currently in practice, the serum albumin level from routinely drawn monthly labs will automatically feed into the electronic centralized nutritional supplement prescribing protocols, from which supplements are then prescribed and administered. The DCI electronic oral nutritional supplement protocol will be used in the same manner as in current practice and follow the same rules for dosing and stoppage for the usual care arm, while protocol-based administration will continue regardless of serum albumin level for the intensive protocol arm. All new patients at the time of dialysis initiation (first dialysis session) will receive an oral nutritional supplement if prescribed the protocol by their physician. The specific supplement is typically based upon what the individual facility has available and on storage space within facilities. For example, one supplement is a frozen protein supplement (BodyQuest Protein Ice Cream) that can only be used in facilities that have adequate space for food freezers.

As a non-blinded study, the treating physicians will be aware of the study allocation of the facility. In facilities assigned to the intensive oral nutritional supplement intervention, an order will be generated in the DCI MIS by DCI Information Services for administration of an oral protein supplement at each dialysis session. Similarly, in patients assigned to the standard oral nutritional supplement intervention, a renewal order of the current supplement protocol will be generated. As with all orders pertaining to in-center hemodialysis care, the order for intensive versus standard nutritional supplement protocol will need to be signed electronically by the physician caring for the patient. If the physician does not sign this order, the patient will not receive nutritional supplements. The physician, regardless of randomization, can elect to discontinue the supplement order at any time.

As is currently done in practice, the dialysis nurse will record in the treatment record that the nutritional supplement has been dispensed and whether and when it was consumed. Supplements should be distributed and consumed within the first 30 minutes of initiation of a dialysis session.

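### Prespecify baseline serum albumin in the primary mortality model instead of leaving adjustment to a secondary analysis that depends on observed imbalance: a cheap improvement, not an error in the plan

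*Combined protocol and SAP*

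**What the plan says.** Section 3.16 defines the primary analysis in one sentence: "The primary outcome will be analyzed per intent-to-treat principles as a time to event analysis". Section 3.9 adds only that a time-to-event model is used, and section 3.9.1 sizes the trial with an unadjusted logrank test. No covariate is listed in any of the three.

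Section 3.16 argues from the large number of patients that "it is unlikely that mortality risk factors will be differentially distributed across treatment arms". It then says "we will evaluate the distribution of key facility and patient factors by allocation group" and that, "if there are differences in these parameters, secondary analyses using multivariable regression will be performed". The factors are not listed, and no rule says what counts as a difference.

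Elsewhere the plan gives albumin a central place:

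- Section 2.1 says that a low level "is a powerful marker of increased mortality risk".
- Section 3.2 makes it the rule that separates the arms. Usual care is a protocol "whereby those with albumin below 3.5 g/dL receive supplement", and the intensive protocol is one "which will prescribe nutritional supplements for all patients at the dialysis facility regardless of serum albumin levels".
- Section 3.2, on implementation, says that "the serum albumin level from routinely drawn monthly labs will automatically feed into the electronic centralized nutritional supplement prescribing protocols".
- Section 3.7 gives albumin its only named analysis role, as a secondary outcome in mediation analyses.

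**The concern.** The argument from patient numbers does not fit the design. About 86 facilities are randomized (3.9.1), blocked only by region and facility size (3.8). Chance imbalance in a risk factor that clusters by facility depends mainly on the number of facilities. Patients also receive the information sheet and agree after their facility has been assigned (3.6, 3.8), and new patients keep entering facilities whose arm is known. Imbalance can therefore come from selection as well as from chance.

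Albumin is the natural covariate by the plan's own account, and using it needs no new data. Without prespecification, a chance or selection difference in albumin stays in the primary estimate, and precision that albumin could supply is not used. Any adjusted result would follow choices of covariates and trigger made after arm-level data had been seen.

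**Working it through.** **1. The plan's own sample size (inputs from 3.9.1).** HR 0.85, two-sided 0.05, 80% power, control hazard 0.173 per year, 3 years without accrual, dropout 0.05 per arm (time unit not stated), ICC 0.01, 65 patients per facility, interim factor 1.017.

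- Events: 4 × (1.960 + 0.842)² / (ln 0.85)² = 1,189.
- Dropout read as 5% per year gives a rate of -ln 0.95 = 0.0513. The probability of an observed death is λ/(λ + 0.0513) × [1 - exp(-3(λ + 0.0513))]. This is 0.378 for usual care (λ = 0.173) and 0.332 for the intensive arm (λ = 0.147), with mean 0.355.
- N = 1,189 / 0.3551 = 3,348 (stated 3,351).
- Clustering: 1 + 64 × 0.01 = 1.64, and 3,351 × 1.64 = 5,496 (stated about 5,500).
- Interim looks: 5,500 × 1.017 = 5,594 (stated 5,597).

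The plan's figures reproduce for the unadjusted test it chose.

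**2. Assumptions the documents do not give.** Albumin SD 0.4 g/dL; mortality 2 to 3 times higher per 1 g/dL lower; albumin ICC 0.02 to 0.05; facility SD of log hazard 0.1 to 0.2. Per SD of albumin the mortality ratio is 2^0.4 = 1.32 to 3^0.4 = 1.55.

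**3. Chance imbalance with 43 facilities of 65 per arm.** In SD units, the SD of the between-arm difference in mean albumin is √{(2/43) × [ICC + (1 - ICC)/65]}.

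| Albumin ICC | SD of difference | 95% limit |
|---|---|---|
| 0.02 | 0.040 | 0.079 |
| 0.05 | 0.055 | 0.107 |
| Individual randomization, √(4/5,590) | 0.027 | 0.052 |

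An imbalance at the 95% limit shifts the log hazard ratio by about that limit times the log mortality ratio per SD. The low end is 0.079 × 0.277 = 0.022, or 14% of |ln 0.85| = 0.163. The high end is 0.107 × 0.439 = 0.047, or 29%. This ignores any balance gained from blocking.

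**4. Power, ignoring clustering.** This is a large-sample calculation with N = 3,351 and the same treatment effect at every albumin level.

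| Mortality ratio per SD | Overall HR 0.85: unadjusted, adjusted | HR 0.85 within albumin level: unadjusted, adjusted |
|---|---|---|
| 1.2 | 80.0%, 80.5% | 79.4%, 80.0% |
| 1.35 | 80.0%, 81.5% | 78.5%, 80.0% |
| 1.5 | 80.0%, 82.8% | 77.2%, 80.1% |
| 2.0 | 80.1%, 87.6% | 71.7%, 80.4% |

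A check with 2,000 simulated Cox analyses gave 79.9% against 82.5% at 1.5, and 80.8% against 89.1% at 2.0.

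**5. Power with clustering.** Simulated trials of 86 × 65 patients over 3 years, with a facility-robust test and the assumptions in step 2.

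*Constant HR 0.85.* Results from 250 trials per setting, unadjusted/adjusted power in %:

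| Mortality ratio per g/dL | ICC 0.02, SD 0.1 | ICC 0.02, SD 0.2 | ICC 0.05, SD 0.1 | ICC 0.05, SD 0.2 |
|---|---|---|---|---|
| 2 | 94.0/94.8 | 68.8/70.4 | 89.6/92.4 | 75.2/76.8 |
| 3 | 88.0/92.0 | 76.8/78.8 | 83.2/88.4 | 70.8/77.2 |

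The gains are 0.8 to 6.4 points. Other runs gave 0.5 to 6.4 (1,500 trials per setting) and about 0.5 to 9 (600 per setting). One power near 80% from 250 trials has a Monte Carlo standard error of √(0.8 × 0.2/250) = 2.5 points. Both models used the same datasets, so the gains are approximate but better determined than that.

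*Effect only in the upper 75% of baseline albumin.* This assumes an HR of 0.77 to 0.78 there and about 0.85 overall. It is motivated by section 3.2, where low-albumin patients are supplemented in both arms and 20-30% receive supplement at any time. With 2,000 trials per setting the gain was -2.4 to +4.1 points, negative in 3 of 8 settings and under 1.2 points in 7 of 8. A run with 600 per setting gave about -3 to +3. The mean unadjusted HR was 0.846 to 0.850 and the mean adjusted HR 0.848 to 0.854.

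*In between.* With 35% of the log hazard ratio given to the low-albumin group, the gain was -0.4 to +4.7 points.

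*Precision.* The empirical standard error fell by 0 to 9% in the 250-trial run. In the 600-trial run, over both effect patterns, it was lower with adjustment in 15 of 16 settings, by up to about 8%.

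**The case against.** An unadjusted intent-to-treat comparison is a legitimate primary analysis, and four stronger readings do not hold.

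- *The trial is underpowered as planned.* The documents do not show this. Step 1 reproduces the stated figures for an unadjusted logrank test at HR 0.85.
- *Leaving albumin out pulls the hazard ratio toward 1 and always costs power.* This needs a treatment effect that is constant across albumin levels, which fits poorly with a design in which low-albumin patients are treated alike in both arms. When the effect was confined to higher albumin, the adjusted hazard ratio was slightly nearer 1 and the power gain was about zero. Even with a constant effect, the gap is one between a marginal and a conditional hazard ratio, not a bias.
- *The primary result depends on what is seen in the data.* It does not. The conditional clause in 3.16 governs only secondary regression, and the primary comparison is run regardless. Nor does the plan say that albumin would be used if imbalanced, since it names no factor even there.
- *Chance facility differences in albumin bias the comparison.* A valid facility-level variance already allows for chance differences. Selection after allocation is not covered in that way.

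It is also fair that the size of the benefit rests on figures from outside the documents. An albumin value at dialysis initiation lies about 90 days before time 0 for incident patients, and patients who transfer in need a rule of their own. Both timing points stand and are dealt with in the fix. None of this removes the precision gain or the protection against imbalance.

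**Conclusion.** The point holds as a cheap improvement. The primary mortality model has no covariates, adjustment is secondary and depends on undefined differences, and the reason given overlooks that about 86 facilities are the randomized units. Baseline albumin is a strong predictor by the plan's own account and is already held.

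On the assumptions in step 2, prespecifying it lowers the standard error by about 0 to 9% and guards against imbalance. A chance imbalance at the 95% limit could otherwise move the log hazard ratio by about 14 to 29% of the target effect. Protection against selection extends only to selection that shows in albumin. The power gain is roughly 1 to 9 points if the effect is the same at all albumin levels, and about zero (roughly -3 to +4 points) if it is confined to patients above the threshold. The documents do not settle which of these applies, so power alone is not the reason to make the change.

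**What to change.** In section 3.16:

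- Include continuous baseline serum albumin in the primary mortality model regardless of observed balance, with facility clustering accounted for. Remove the imbalance condition for albumin.
- Define baseline as the last routine value before facility randomization for prevalent patients, the first value at dialysis initiation for incident patients, and the last value before entry to the facility for patients who transfer in. The initiation value precedes any difference in exposure. It therefore does not depend on how long both arms are supplemented, which 3.13 and 3.16 give as 90 days and 3.9.1 as 90 to 120 days; those passages should be reconciled.
- Never use follow-up albumin in this model, because section 3.7 treats it as a possible mediator.
- State that the hazard ratio is conditional on albumin, and report the unadjusted estimate alongside.
- State a simple rule for missing baseline values, such as single imputation or a missing indicator.

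The cost is a few sentences of SAP text and one variable already in the electronic record. No extra data, patients or changes in care are needed. The downsides are a few missing values and a conditional rather than marginal hazard ratio.
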